tabularising and rearranging according to thematic content in summary form. The final stage will involve mapping and interpretation to explore the relationships between the concepts connecting the TFA with the charted data; an example of this is found in Western et al.'s (2023) study on an intervention for pre-frail individuals. Some 'open coding' will also be carried out to ensure no important data are missed from the analysis (Gale et al., 2013).

In terms of quantitative data obtained from the stroke survivor participants, the degree of acceptability will be calculated by calculating the mean ratings for responses to each of the seven TFA constructs on the acceptability questionnaire measure, the mean rating for the general acceptability item (item 10), and the total mean rating of all items. For two of the seven constructs, Sekhon et al., (2022) suggest a choice of two questions, whereas all other constructs have only one question. For these two constructs, it has been decided that both of the suggested questions would be included in the acceptability questionnaire used in this study, as it was felt that the questions were different enough from one another that they would both be helpful to ask. For example, the generic TFA questionnaire suggests either 'How fair is [Intervention] for [people/ participants/ recipients] with [condition]?' or 'There are moral or ethical consequences [behaviour *i.e. to engage with*] [intervention]' as questions to measure the construct of ethicality.

To improve the sensitivity to context (Yardley, 2000) the researchers will keep reflective diaries of the data analysis process to ensure that consideration is taken of their role in the research and the analysis and to increase awareness of how this, as well as their existing knowledge, experiences and assumptions, may influence the analysis.

References

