Ethicality The extent to which the intervention has good fit with an individual's value system	
How fair is [Intervention] for [people/ participants/ recipients] with [condition]?
 
 
 Very unfair	Unfair	No opinion	Fair	Very fair	
 
 1	2	3	4	5	
 
 
OR
 
There are moral or ethical consequences [behaviour i.e. to engage with] [intervention]
 
 
 Strongly disagree	Disagree	No opinion	Agree	Strongly agree	
 
 1	2	3	4	5	
 
	Very unfair	Unfair	No opinion	Fair	Very fair	1	2	3	4	5	Strongly disagree	Disagree	No opinion	Agree	Strongly agree	1	2	3	4	5	
Depending on the context of the intervention and behaviours associated with the intervention one of the two items should be used.

Very unfair	Unfair	No opinion	Fair	Very fair																		
1	2	3	4	5																		
Strongly disagree	Disagree	No opinion	Agree	Strongly agree																		
1	2	3	4	5																		
Perceived effectiveness The extent to which the intervention is	The [intervention] has improved [behaviour/ condition/ clinical outcome]:	
This item should relate to the primary outcome variable in the main trial/study, thus the item will be intervention
																				

perceived to have achieved its objective						specific. E.g. quality of life, walking ability										
Intervention coherence The extent to which the participant understands how the intervention works	It is clear to me how [intervention] will help [manage/improve] my [behaviour/ condition/clinical outcome]					*In some studies, researchers may want to include an option for participants to provide more information for this item.										
	
 
 Strongly disagree	Disagree	No opinion	Agree	Strongly agree	
 
 1	2	3	4	5	
 
 
*Please tell us more about your views
					Strongly disagree	Disagree	No opinion	Agree	Strongly agree	1	2	3	4	5	This will depend on the resources of the study for analysing qualitative data and whether having more information will be relevant.
Strongly disagree	Disagree	No opinion	Agree	Strongly agree												
1	2	3	4	5												

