Self-efficacy A participant's confidence that they can perform behaviour(s) required to participate in the intervention	How confident did you feel about [behaviour i.e. engaging with] [intervention]?															
	
 
 Very unconfident	Unconfident	No opinion	Confident	Very confident	
 
 1	2	3	4	5	
 
					Very unconfident	Unconfident	No opinion	Confident	Very confident	1	2	3	4	5	
Very unconfident	Unconfident	No opinion	Confident	Very confident												
1	2	3	4	5												
Opportunity costs The benefits, profits or values that would have to be given up to engage with the intervention	[Behaviour i.e. engaging in] [intervention] interfered with my other priorities															
	
 
 Strongly disagree	Disagree	No opinion	Agree	Strongly agree	
 
 1	2	3	4	5	
 
					Strongly disagree	Disagree	No opinion	Agree	Strongly agree	1	2	3	4	5	
Strongly disagree	Disagree	No opinion	Agree	Strongly agree												
1	2	3	4	5												
General acceptability	How acceptable was the [intervention] to you?					The general acceptability item has been included as in some instances, an overall acceptability item may be useful and to allow for researchers to explore which of the 7 TFA constructs influences/ drives participants' general acceptability judgment.										
	
 
 Completely unacceptable	Unacceptable	No opinion	Acceptable	Completely acceptable	
 
 1	2	3	4	5	
 
					Completely unacceptable	Unacceptable	No opinion	Acceptable	Completely acceptable	1	2	3	4	5	
Completely unacceptable	Unacceptable	No opinion	Acceptable	Completely acceptable												
1	2	3	4	5												

Note. From "Development of a theory-informed questionnaire to assess the acceptability of healthcare interventions" by M. Sekhon, M. Cartwright and J. J. Francis. Sekhon, 2017, *BMC Health Services Research*, 22(279), supplementary file 7(<https://doi.org/10.1186/s12913-022-07577-3>). CC BY 4.0 <http://creativecommons.org/licenses/by/4.0/>)

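### The total mean over all ten questionnaire items gives the seven acceptability constructs unequal weights, mixes in the general item, and has no stated rule for item direction

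*Combined protocol and SAP*

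**What the plan says.** The Analysis section of the protocol defines the degree of acceptability by three descriptive figures: "the mean ratings for responses to each of the seven TFA constructs on the acceptability questionnaire measure", then "the mean rating for the general acceptability item (item 10"), and finally "the total mean rating of all items".

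The source instrument offers a choice of two questions for two constructs, "whereas all other constructs have only one question". For those two, the plan decides that "both of the suggested questions would be included in the acceptability questionnaire used in this study", because the questions were judged different enough for both to be useful. Appendix E shows that the two constructs are affective attitude and ethicality. For each of them its note says that only one "of the two items should be used".

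Appendix E also explains the general acceptability item: an overall rating may be useful in some settings, and it lets researchers "explore which of the 7 TFA constructs influences/ drives participants' general acceptability judgment".

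The section on research questions operationalises acceptability as the seven constructs and ranks none of them above the others. The plan states no weighting, no averaging within a construct before the total is formed, no exclusion of the general item from the total, and no reverse-scoring. The Quantitative Data section mentions only the construct means.

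**The concern.** The reason given for keeping both questions justifies asking them. It does not justify letting affective attitude and ethicality each count twice as much as burden or opportunity costs in a summary. The weights come from the number of questions per construct, not from a view of what matters for acceptability.

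The general item is a different kind of quantity. In Appendix E it is a summary judgement that the constructs are meant to explain. Averaging it with them blends the judgement with its proposed drivers.

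The raw mean may also combine items that run in opposite directions, so that good and bad responses partly cancel.

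What is at stake is one of the three figures offered for the degree of acceptability. A single total is easily quoted on its own, and the acceptability finding informs whether the intervention needs further adaptation, or replacement, before the later feasibility trial.

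**Working it through.** **Inputs.** The Analysis section gives two constructs with two items each, five with one item each, and one general item numbered 10. Appendix E gives the 1–5 response scales. The response scales for burden and perceived effectiveness do not appear in the text available to me. I assume 1–5 for both, and high = favourable for effectiveness.

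**1. Item count.** 2 × 2 + 5 × 1 + 1 = 10. This reproduces the plan's numbering of the general item.

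**2. Weights.** Weight = items per construct ÷ 10.

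| Component | Total as written | Mean of seven construct scores |
|---|---|---|
| Affective attitude | 2/10 = 20% | 1/7 = 14.3% |
| Ethicality | 2/10 = 20% | 14.3% |
| Each of the other five constructs | 1/10 = 10% | 14.3% |
| General item | 1/10 = 10% | 0% |

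The two paired constructs together carry 40% rather than 2/7 = 28.6%.

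**3. Largest possible gap, items aligned so that high is favourable.** The gap is greatest when the paired constructs and the general item sit at one end of the scale and the other five at the other end.
- Paired and general items at 5, others at 1: total = (4 × 5 + 5 × 1 + 5)/10 = 3.00; seven-construct mean = (2 × 5 + 5 × 1)/7 = 2.14; gap = +0.857.
- The mirror image: total = (4 × 1 + 5 × 5 + 1)/10 = 3.00; seven-construct mean = (2 × 1 + 5 × 5)/7 = 3.86; gap = −0.857.

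If the general item is left out of the total but the paired items still count separately, the first case gives (4 × 5 + 5 × 1)/9 = 2.78 against 2.14, a gap of 0.635. Dropping the general item alone therefore does not remove the problem.

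**4. A milder illustration (assumed ratings).** Paired constructs and general item 4.5, other five constructs 3.5:
- Total = (4 × 4.5 + 5 × 3.5 + 4.5)/10 = 4.00.
- Seven-construct mean = (2 × 4.5 + 5 × 3.5)/7 = 3.79.
- Gap = +0.21, of which 0.114 comes from the double weight and 0.100 from the general item.

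With the pattern reversed, the total is (4 × 3.5 + 5 × 4.5 + 3.5)/10 = 4.00 and the seven-construct mean is (2 × 3.5 + 5 × 4.5)/7 = 4.21, a gap of −0.21. With equal ratings throughout, the gap is zero.

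**5. Item direction.** In Appendix E, strong agreement (5) with the opportunity-cost item means that taking part got in the way of other priorities, which is unfavourable. Strong agreement with the second ethicality item means that there are moral or ethical consequences, which is plausibly unfavourable. If raw scores are averaged and these two items run opposite to the other eight:
- Fully favourable respondent: (8 × 5 + 2 × 1)/10 = 4.2, not 5.0.
- Fully unfavourable respondent: (8 × 1 + 2 × 5)/10 = 1.8, not 1.0.

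If the burden item also scores high when unfavourable, which is an assumption, the figures are (7 × 5 + 3 × 1)/10 = 3.8 and (7 × 1 + 3 × 5)/10 = 2.2.

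Equal construct weights alone do not cure this. With the two reversed items left raw, the favourable respondent's ethicality mean is (5 + 1)/2 = 3.0, and the seven-construct mean is (5 + 5 + 3 + 5 + 5 + 5 + 1)/7 = 4.14.

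**The case against.** The strongest reply is that the same sentence of the plan already reports each construct mean and the general item. A poor rating for burden or opportunity costs would be visible beside the total. The Design section says the questionnaire is there to show where acceptability is strong or weak, which is a construct-level purpose. The total has no threshold, test or progression rule, and it describes about ten people alongside focus groups built on the same framework. All of this stands, and it limits the consequence.

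It can also be said that equal construct weights are themselves a choice. Appendix E prescribes no total and does not bar the general item from one, and keeping both paired questions is a disclosed, reasoned departure. This stands in part. Other weights could be defended, but the plan defends none, and equal weights are the natural default for a definition made of seven unranked constructs.

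A reader might go further and infer that the total leans towards liking and fairness and hides the demands of a travel-heavy programme. The documents do not support that. The lean needs a particular pattern of ratings on aligned items; the reverse pattern changes its sign, and in raw scores the second ethicality item could offset the fairness item. The protocol does anticipate time burden and fatigue, but it plans four weekly visits with reimbursable parking and gives no evidence of how participants will rate them.

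Finally, the study questionnaire is adapted from the generic form, and only the generic form is appended. The final wording and direction of its items cannot be confirmed.

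**Conclusion.** The point holds as a scoring defect of modest consequence. The 20/20/10 weights and the inclusion of the general item follow directly from the text. The bound of 0.857 points assumes only aligned items scored 1–5; the 0.21-point illustration rests on assumed ratings. The sign of any difference is unknown in advance. The direction problem is firm for the opportunity-cost item as worded in the generic form, plausible for the second ethicality item, and not assessable for burden.

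A reader might infer that the study's answer on acceptability is in doubt. It is not: the construct means, the general item and the focus-group analysis do not depend on the total, although the construct means need the same statement of item direction. The total should still be defined properly, because the plan offers it as a measure of the degree of acceptability.

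**What to change.** In the Analysis section, replace the total over all items with a rule in four parts:
1. State the direction of each item in the study questionnaire and code every item so that high is favourable, reverse-scoring where needed.
2. Average the two items within affective attitude and within ethicality to give one score per construct.
3. Define the total as the mean of the seven construct scores.
4. Report the general acceptability item on its own, outside the total, and show the four paired items individually.

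Appending the adapted questionnaire would let readers confirm the coding. The cost is a few sentences in the Analysis section, with no new data and no added burden on participants. It is best settled before any ratings are seen, so that the scoring is not chosen after the fact.

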Appendix A

Theoretical Framework of Acceptability

Theoretical Framework of acceptability (TFA)	Definition
Ethicality	The extent to which the intervention has good fit with an individual's value system
Affective Attitude	Anticipated Affective Attitude: How an individual feels about the intervention, prior to taking part Experienced Affective Attitude: How an individual feels about the intervention, after taking part
Burden	Anticipated burden: The perceived amount of effort that is required to participate in the intervention Experienced burden: the amount of effort that was required to participate in the intervention
Opportunity Costs	Anticipated opportunity cost : The extent to which benefits, profits, or values must be given up to engage in the intervention Experienced opportunity cost: the benefits, profits or values that were given up to engage in the intervention
Perceived effectiveness	Anticipated effectiveness: the extent to which the intervention is perceived to be likely to achieve its purpose Experienced effectiveness: the extent to which the intervention is perceived to have achieved its intended purpose
Self-efficacy	The participant's confidence that they can perform the behaviour(s) required to participate in the intervention
Intervention Coherence	The extent to which the participant understands the intervention and how it works

Note. From "Acceptability of healthcare interventions: An overview of reviews and development

of a theoretical framework" [Supplementary File 6] by M. Sekhon, M. Cartwright and J. J.

Francis. Sekhon, 2017, *BMC Health Services Research*, 17(1):88,

(<https://doi.org/10.1186/s12913-017-2031-8>). CC BY 4.0

(<http://creativecommons.org/licenses/by/4.0/>)

Appendix B

Example draft session plan for sCST

Topic - Current Affairs

- Introduction
 - Welcome all to the group by name, name labels.
 - Group rules – confidentiality and respect. Sometimes we might slip up and make mistakes but that's ok, it is important to discuss that privately.
 - Come up with group name
 - Come up with group song – YouTube backing track
 - Orientation – what is the date? Errorless learning? On this day discussion
 - One key headline/news event discussion
- Main activity
 - What possession do you treasure the most?
 - Boomers, Gen x, Millenials, Gen z
 - Fashion
 - Where would you to visit?
 - Social media? Case study use of twitter for good?
- Closing
 - Psycho-ed about summaries as a memory strategy/ rehearsal of information
 - Bullet points – what have you learned during the session or what surprised you?
- Take-home activity
 - Practise the summarising technique, find a news story you find interesting or enjoyable, discuss it with your carer and practise together summarising key points

Appendix C

Clinical Frailty Scale

Box 1: The CSHA Clinical Frailty Scale

- 1 *Very fit*— robust, active, energetic, well motivated and fit; these people commonly exercise regularly and are in the most fit group for their age
- 2 *Well*— without active disease, but less fit than people in category 1
- 3 *Well, with treated comorbid disease*— disease symptoms are well controlled compared with those in category 4
- 4 *Apparently vulnerable*— although not frankly dependent, these people commonly complain of being “slowed up” or have disease symptoms
- 5 *Mildly frail*— with limited dependence on others for instrumental activities of daily living
- 6 *Moderately frail*— help is needed with both instrumental and non-instrumental activities of daily living
- 7 *Severely frail*— completely dependent on others for the activities of daily living, or terminally ill

Note: CSHA = Canadian Study of Health and Aging.

Note. From “A global clinical measure of fitness and frailty in elderly people” by K. Rockwood, X. Song, C. MacKnight, H. Bergman, D. B. Hogan, I. McDowell, A. Mitnitski, 2005, *CMAJ*, 173(5), p. 490 (<https://doi.org/10.1503/cmaj.050051>) Copyright 2005 by CMA Media Inc. or its licensors

Appendix D

Example Focus Group Topic Guide (Draft)

Please note, this is a draft topic guide for the stroke survivor participants. Development of topic guides is ongoing, with input from PPI volunteers.

Research goals of the focus group:

- How would pre-frail stroke survivors feel about adapted CST as an intervention?
- What do pre-frail stroke survivors think about the amount of effort that would be required to participate in an adapted CST intervention?
- What, if any, ethical consequences did pre-frail stroke survivors feel there might be to engaging in an adapted CST intervention?
- What did pre-frail stroke survivors see as the potential costs of engaging in an adapted CST intervention?
- How effective do pre-frail stroke survivors think an adapted CST intervention could be?
- How confident do pre-frail stroke survivors feel about engaging in an adapted CST intervention?
- How well do pre-frail survivors understand the adapted CST intervention and how it works?

Introduction – approximately 10 minutes:

- *Welcome, introduction of the focus group*
- *Instructions regarding the focus group:* “I am interested in how you felt about the sample sessions of adapted CST that you tried and how you would feel about the idea of attending a full programme of perhaps 14 weekly sessions”
- *Ground rules:* “I will ask a number of questions, and I would like to hear from as many of you as possible for each question. It would be helpful for me if only one person speaks at a time so please wait until one person is finished before the

next person speaks. If you are able to use the 'hands up' button, it would be helpful if you can press this when you have something to say and I will then invite you to speak. Please be respectful of one another, every opinion is valid and helpful. Please be honest because your comments will help us to know what works well and what we might need to change in order to make it better. We will take a break half way through so you can go to the loo or get a drink, but if you need to step out at any point before or after this break please go ahead – just turn off your camera and microphone and turn them on again when you come back"

Main questions – approximately 90 minutes:

- "To start us off, could you please each tell me one word that you feel summarises what you thought of the eight sample sessions you had?"
- "Thank you, let's talk a bit more about how you felt about the sessions you tried"
 - What did you like about the sessions?
 - What did you not like?
 - What did you find difficult about the sessions or the process of attending the sessions?
 - Did you find the activities enjoyable?
 - What did you think was the purpose of the activities? And do you think that the activities helped you in any way?
 - Did you gain anything from coming to these sessions?
 - Were there any negatives to coming to these sessions?
 - Did the sessions feel relevant to the difficulties you experience after your stroke?
 - Thinking back to before the sessions, how did you feel about attending the first one?

~Comfort break – 10 minutes~

- Now I would like to ask you a few questions about how you would feel about

attending a full course of sessions like these, perhaps 14 sessions once a week?

- Do you think there would be any benefits to attending a full course of this intervention? If so what do you think the benefits could be?
- (if not mentioned – do you think this intervention would have any effect on your ability to complete your usual day-to-day tasks/your mood/your memory and thinking skills?)
- Do you think a full course of this intervention would help you to achieve your goals?
- What would be the barriers or challenges involved in attending a full course of this intervention?

- Finally, I want to ask you about any changes or improvements that might be needed
 - Is there anything you would change about the general format of the sessions? (e.g. length, frequency, session structure)
 - Is there anything you would change to the content/themes of the sessions?
 - Is there anything missing that you feel would be helpful?
 - Is there anything you would change about the types of activities included in the sessions?

Conclusion – approximately 10 minutes:

- *Sum up what has been discussed, mention the positive aspects, compliment and thank the participants*
 - “Is there anything important to you we haven't mentioned?”
 - “If you want to follow any issues you have talked about, you can contact myself or my supervisor via email”
 - “We will shortly send you a debrief letter which will explain your options about withdrawing from the study, raising concerns, and how you can be updated on the results of the study. You will also receive a £10 shopping voucher.”

